### 7.2 Sample Size Calculation

H0: The null hypothesis is that the overall response rate (ORR) is similar to historical result of immunotherapy, i.e. 20%

H1: The alternative hypothesis of treatment efficacy: experimental treatment with bintrafusp alfa would result in 40% ORR.

To detect 20% of differences from 20% to 40% in the number of patients proceeding to surgery, with Type I error of 0.05 and 80% power, the target sample size is 33 patients.

Modified Simon's two-stage optimal design will be used. In the first stage, 18 patients will be enrolled. If there are 4 or fewer responses in these 18 patients, the study will be stopped. Otherwise, 15 additional patients will be accrued for a total of 33 valid cases. The null hypothesis will be rejected if 11 or more responses are observed in 33 patients and the treatment will be considered worthy of further investigation. Patients may drop out before their objective response can be assessed. Such patients will be excluded for the ORR assessment and will be replaced by other patients that the objective response can be assessed. The study will be continued until the first or the second stage evaluation is achieved. Assuming 10% drop out rate, 38 patients will be accrued initially. We assume 50% of screened population will be eligible for the study, thus we plan to screen for 76 patients.

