## 2.5 Study Participants

A total of 38 patients will be accrued to assess the potential benefit of bintrafusp alfa.

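### Accruing 38 patients at the outset, and as an unconditional total, does not fit the 18-then-33 two-stage rule, and the only cut-off is for 33 assessable patients

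*Protocol*

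**What the plan says.** Protocol 7.2 tests a 20% response rate against 40%. It states the design's properties as "with Type I error of 0.05 and 80% power, the target sample size is 33 patients". The size of stage 1 is given by "In the first stage, 18 patients will be enrolled", and the futility rule attached to it reads "If there are 4 or fewer responses in these 18 patients, the study will be stopped". If the trial goes on, a further 15 bring it to 33 valid cases. The final rule is "The null hypothesis will be rejected if 11 or more responses are observed in 33 patients". Patients who leave before response can be assessed are excluded from the response rate and replaced, and the study runs on until the evaluation for the stage is reached.

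The same section then says "Assuming 10% drop out rate, 38 patients will be accrued initially". Section 2.5 says "A total of 38 patients will be accrued to assess the potential benefit of bintrafusp alfa", with no condition. Section 7.3 ties its toxicity rule to the recruitment of these same 38 patients.

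**The concern.** Accrual beyond stage 1 cannot both depend on the stage-1 result and be completed at the outset. Replacing dropouts as they occur and enrolling a fixed surplus in advance are also two different ways of reaching 33, and the protocol states both. It does not say that 38 is a planning figure, that stage 2 waits for the stage-1 look, or which 33 patients are tested if more than 33 prove assessable.

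Two things are at stake. One is the trial's only futility stop: if 38 were enrolled before the look, up to 38 − 18 = 20 further patients would be treated where the plan intended a stop. The other is the primary decision: if more than 33 patients are assessable, the denominator or the cut-off could be settled after the responses are known.

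**Working it through.** **Inputs, all from protocol 7.2.** p0 = 0.20, p1 = 0.40; n1 = 18, stop at 4 or fewer; n = 33, reject at 11 or more; dropout 10%; accrual 38.

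**1. Reproduce the plan's own figures.** With X1 ~ Bin(18, p) and X2 ~ Bin(n − 18, p):

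P(reject) = Σ over x = 5,…,18 of P(X1 = x) · P(X2 ≥ 11 − x)

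At n = 33 this gives 0.0458 for p = 0.20 and 0.801 for p = 0.40. The stated 0.05 and 80% are met. A 5% response-count rule of this kind is one-sided.

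**2. What the stage-1 stop does.** P(X1 ≤ 4) = 0.716 at p = 0.20 and 0.094 at p = 0.40. If the drug is no better than the historical rate, the trial stops at 18 with probability 71.6%. Enrolling 38 before the look would lose that protection.

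**3. Dropout allowance.** 33 / 0.90 = 36.7, so 37 patients. Going from 38 to 33 is a loss of 5 / 38 = 13.2%, not 10%.

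**4. Assessable patients out of 38 at 10% dropout.** The expected number is 38 × 0.90 = 34.2. With the number of dropouts D ~ Bin(38, 0.10):

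- P(D ≤ 4), so 34 or more assessable: 0.670
- P(D = 5), so exactly 33: 0.155
- P(D ≥ 6), so fewer than 33 without further replacement: 1 − 0.670 − 0.155 = 0.175

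On the plan's own assumption, more than 33 is the likely result if all 38 are accrued.

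**5. What carrying the cut-off of 11 beyond 33 would do.** Same formula, stage-1 stop kept:

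| Assessable n | Type I error | Power |
|---|---|---|
| 33 | 0.0458 | 0.801 |
| 34 | 0.0544 | 0.825 |
| 35 | 0.0636 | 0.844 |
| 36 | 0.0733 | 0.859 |
| 37 | 0.0835 | 0.870 |
| 38 | 0.0939 | 0.879 |

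If the stage-1 stop were not applied, the error with a cut-off of 11 would be P(Bin(n, 0.20) ≥ 11): 0.0508 at 33 and 0.1219 at 38. This is a different scenario and should not be mixed with the table.

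**6. Would other cut-offs serve?** With the stage-1 stop kept:

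| Cut-off | n | Type I error | Power |
|---|---|---|---|
| 12 | 34 | 0.0255 | 0.746 |
| 12 | 35 | 0.0313 | 0.777 |
| 12 | 36 | 0.0378 | 0.804 |
| 12 | 37 | 0.0449 | 0.826 |
| 12 | 38 | 0.0526 | 0.844 |
| 13 | 38 | 0.0259 | 0.782 |

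Both targets are met only at 36 and 37. At 34, the expected number, power falls to 0.746.

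**The case against.** The strongest reply is that the protocol already fixes the test. It names 33 valid cases, excludes and replaces patients who cannot be assessed, and makes stage 2 conditional on the stage-1 result. On that view 38 is simply 33 enlarged for dropout, placed beside the screening figure, and *initially* is a loose word that does not tell the site to enrol 38 before the look. Handling of surplus patients could also sit in an analysis plan that is not shown.

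Much of this stands. A reader might infer that the plan applies 11 responses to as many as 38 patients and so nearly doubles its type I error. The document does not support that. No section attaches the cut-off of 11 to any number but 33, and under the written rule the error stays at 0.0458. The value 0.094 needs no dropout at all and a cut-off carried over from 33; at the planned dropout the same misuse gives about 0.054. Nor would extra assessable patients cost power with a cut-off of 11; power rises.

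What does not stand is that nothing needs changing. Accrual and the decision boundary are fixed in the protocol itself, which gives 38 as initial in 7.2, as an unconditional total in 2.5 and as the recruited number in 7.3. Reading it as a planning figure is plausible, but the text does not say so. Even on that reading, nothing identifies the 33 patients to be tested if 34 or more are assessable. The gap between 37 and 38 is one patient and matters little.

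**Conclusion.** The point holds as an inconsistency in the accrual rules, not as an error in the test. The rule of 4 in 18 and 11 in 33 delivers what the plan claims. The mentions of 38 in 2.5, 7.2 and 7.3 do not fit it. Taken literally, they would defeat a futility stop that has a 71.6% chance of acting under the null. At the plan's own dropout rate they would also leave 34 or more assessable patients with probability 67%, against a cut-off defined only for 33.

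Inflation to 0.054–0.094 is conditional: it needs more than 33 assessable patients, an unchanged cut-off of 11 and the stage-1 stop in force. The 67% assumes that dropouts are independent at exactly 10% and that all 38 are accrued. The ambiguity affects the primary decision and the only futility look, so it should be resolved, and a few sentences are enough.

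**What to change.** In 2.5 and 7.2, replace both statements about 38 with wording such as: *About 38 patients are planned in total, allowing for replacement of non-assessable patients. Accrual to stage 2 opens only after at least 5 responses among the first 18 assessable patients.* Add to 7.2: *The primary test uses the first 33 assessable patients in order of enrolment, with the cut-off of 11 responses; any further patients are reported descriptively.*

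*Assessable* is needed in both places so that the text agrees with the exclude-and-replace rule. *About* is needed because replacement may take the total past 38. Bring the reference to 38 in 7.3 into line with the revised accrual wording. Correct either the dropout rate or the number: 10% gives 37, while 38 corresponds to about 13%.

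Do not add cut-offs of 12 or 13 for larger denominators. A cut-off of 12 drops power below 80% at 34 and 35, and at 38 its error is 0.0526; a cut-off of 13 at 38 drops power to 0.782.

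The cost is a wording amendment. It needs no extra patients, and the type I error of 0.0458 and power of 0.801 are kept.

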### **7.3 Early Stopping Rule**

Excessive toxicity will also be monitored. Assuming no more than a 10% SAE rate on historical treatment, the increase of treatment-related SAE to a rate of 30% or greater in the studied treatment will be considered unacceptable, and the study will be then stopped prematurely and will early stop the trial if treatment related SAE >30%. Upon the recruitment of these 38 patients, if 10 or more patients had treatment-related SAE, the study will be stopped. The corresponding lower bound of exact one-sided 90% confidence interval is 30.5%.

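### Toxicity stopping rule: the stated 30.5% lower bound is impossible for 10 of 38 patients (26.3%; correct bound 17.0%), and the count of 10 does not match the >30% criterion beside it

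*Protocol*

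**What the plan says.** Section 7.3 of the protocol (Early Stopping Rule) takes a historical SAE rate of at most 10% as its reference ("Assuming no more than a 10% SAE rate on historical treatment") and then states the toxicity limit in four ways:

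- as a principle: "the increase of treatment-related SAE to a rate of 30% or greater in the studied treatment will be considered unacceptable";
- as a trigger on a rate: the sponsor "will early stop the trial if treatment related SAE >30" (per cent);
- as a trigger on a count: "Upon the recruitment of these 38 patients, if 10 or more patients had treatment-related SAE, the study will be stopped";
- as a confidence statement attached to that count: "The corresponding lower bound of exact one-sided 90% confidence interval is 30.5" (per cent).

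The denominator of 38 is not a slip confined to this paragraph. Section 2.5 says "A total of 38 patients will be accrued to assess the potential benefit of bintrafusp alfa", and section 7.2 says "Assuming 10% drop out rate, 38 patients will be accrued initially".

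**The concern.** The lower confidence bound offered for 10 of 38 is larger than 10/38 itself, which no interval method allows. The bound is the only statistical support given for the count. It tells an ethics committee that reaching the trigger means the treatment-related SAE rate exceeds 30% with 90% confidence. If that is false, the committee is misinformed about the evidence on which a safety decision would rest.

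The count and the rate trigger also point to different numbers of patients. Someone applying the paragraph cannot tell whether 10 was meant to implement the 30% limit, or whether the count, the denominator or the bound was carried over from another calculation.

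**Working it through.** **Inputs (section 7.3):** count x = 10; denominator n = 38; exact one-sided 90% interval, so alpha = 0.10; stated bound 30.5%; unacceptable rate 30%; historical rate 10%. The 20% rate used below is an intermediate value chosen for illustration.

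**1. Attempt to reproduce the stated bound.** The exact (Clopper-Pearson) lower bound is the alpha quantile of a Beta(x, n − x + 1) distribution.

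- Point estimate: 10/38 = 26.3%.
- Lower bound: 0.10 quantile of Beta(10, 29) = 0.1704, or 17.0%. As a check, P(X ≥ 10 | n = 38, p = 0.1704) = 0.100.

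The stated 30.5% is not reproduced. Other choices do not reach it either:

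| Calculation for 10 of 38 | Result |
|---|---|
| Exact lower bound, one-sided 95% | 15.0% |
| Exact lower bound, one-sided 97.5% | 13.4% |
| Mid-P lower bound, 90% | 18.0% |
| Wald lower bound, 90% | 17.2% |
| Wilson lower bound, 90% | 18.3% |
| Exact upper bound, one-sided 90% | 37.6% |

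**2. Could another count or denominator have been meant?** With n = 38 the exact 90% lower bounds are:

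| x of 38 | Observed rate | Lower bound |
|---|---|---|
| 10 | 26.3% | 17.0% |
| 11 | 28.9% | 19.3% |
| 12 | 31.6% | 21.6% |
| 15 | 39.5% | 28.7% |
| 16 | 42.1% | 31.1% |

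No count gives 30.5%. With the 33 evaluable patients of section 7.2, 10/33 = 30.3% has a lower bound of 19.8%. A bound of 30.5% does arise for 14/33 and for 10/22, but the protocol states neither pair, so this can only hint at where the figure came from.

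**3. What 10 of 38 does support.** The confidence level at which its lower bound equals 30% is 1 − P(X ≥ 10 | 38, 0.30) = 1 − 0.7449 = 0.2551, or 25.5%.

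**4. The count against the >30% wording.** Since 0.30 × 38 = 11.4, an observed rate above 30% first occurs at 12 patients. If the wording is instead read as a lower bound above 30%, it is first met at 16. Neither reading gives 10.

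Exact binomial probabilities for a single look at n = 38:

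| True rate | P(X ≥ 10) | P(X ≥ 12) | P(X = 10 or 11) |
|---|---|---|---|
| 10% | 0.00340 | 0.00022 | 0.3% |
| 20% | 0.21553 | 0.06231 | 15.3% |
| 30% | 0.74488 | 0.47640 | 26.8% |

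The last column is the difference of the two before it, for example 0.74488 − 0.47640 = 0.26848. It is the probability of a result at which the count says stop while the observed rate is not above 30%. Under the lower-bound reading the gap covers 10 to 15 events, with probabilities 0.3%, 21.4% and 66.9%.

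**The case against.** The strongest reply is that the count is what operates. Ten or more of 38 is explicit, can be carried out, and stops no later than either reading of the >30% wording. On that view the wrong bound is faulty justification and leaves patients no less protected. The two triggers can also be read as separate sufficient conditions, since neither sentence says the study continues below its threshold. All of this is fair. Staff do not receive opposite orders: the mismatch is between two thresholds presented as one rule. It does not rescue the bound, which remains false, and the text does not explain why the count fires at 26.3% when the rate called unacceptable is 30%.

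Three narrower points also have weight. The lower-bound reading of >30% is suggested only by the sentence that carries the error, so the comparison of 10 with 12 is the firmer one. The probabilities above assume one look at exactly 38 patients, whereas section 7.2 allows a futility stop after 18 and replacement of patients not assessable for response. And "the study will be then stopped prematurely" can coexist with a count read once all 38 are recruited, because treatment and follow-up each run for up to 2 years. That last matter is one of wording only.

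The statistical analysis plan, which is not at hand, could add detail. It could not make 30.5% a lower bound for 10 of 38.

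**Conclusion.** The concern holds. The bound in section 7.3 is wrong as written: 17.0% instead of 30.5% for 10 of 38, and impossible under any interval method because it exceeds the observed 26.3%. The implied 90% confidence that the rate exceeds 30% is in fact 25.5%. Separately, the count of 10 does not correspond to the >30% trigger, which as an observed rate needs 12 of 38. The two differ with probability 0.3%, 15.3% and 26.8% at true rates of 10%, 20% and 30%.

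The bound result depends only on the count, denominator and confidence level printed in the section. The probabilities assume independent patients and a single assessment at 38. Because a safety threshold is supported by a false figure, this must be corrected. The primary ORR analysis is not affected.

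**What to change.** Rewrite section 7.3 so that the count, the denominator, the rate wording and the confidence bound describe one rule. Which threshold to adopt is for the sponsor to decide.

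- If 10 of 38 is kept: give the exact one-sided 90% lower bound as 17.0%, remove the implication of 90% confidence that the rate exceeds 30%, and align the >30% sentence with the count. It would also help to state the stopping probabilities (0.3%, 21.6% and 74.5% at true rates of 10%, 20% and 30%) and that they assume one look at 38.
- If another count or denominator was intended: state it with its own bound.
- In either case, make clear when the count is read, so that premature stopping and a count taken after full recruitment fit together.

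The cost is one corrected paragraph. It needs no new data and no change to the ORR test. If 10 of 38 is kept, the stated assurance becomes less favourable.

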## **8 ETHICAL, REGULATORY & STUDY OVERSIGHT CONSIDERATIONS**

### **8.1 Responsibilities of the Investigator(s)**

The Investigator(s) undertake(s) to perform the clinical study in accordance with this clinical study protocol, ICH guideline for Good Clinical Practice (GCP) (ICH E6 R2 Step 4) approved on November 9, 2016) and applicable regulatory requirements in Hong Kong. These documents state that the informed consent of the subjects is an essential precondition for participation in the clinical study.

### **8.2 Subject Information**

An unconditional prerequisite for a patient participating in the study is his/her written informed consent. Adequate information must therefore be given to the subject by the Investigator(s) before informed consent is obtained. A person designated by the Investigator(s) may give the information, if permitted by local regulations. A subject information sheet in the local language and prepared in accordance with Good Clinical Practice will be provided by the Investigator(s) for the purpose of obtaining informed consent. In addition to this written information, the Investigator(s) or his/her/their designate will inform the subject verbally. In doing so, the wording used will be chosen so that the information can be fully and readily understood by laypersons.

The patient information sheet will be revised whenever important new information becomes available that may be relevant to the consent of patients.

### **8.3 Informed Consent**

The consent of the patient to participate in the clinical study has to be given in writing before any study-related activities are carried out. It must be signed and personally dated by the patient and by the Investigator(s)/person designated by the Investigator(s) to conduct the informed consent discussion.

Provision of consent will be confirmed in the case report form (CRF) by the Investigator(s). The signed and dated declaration of informed consent will remain at the Investigator(s)'s site and must be safely archived by the Investigator(s) so that the forms can be retrieved at any time for monitoring, auditing and inspection purposes. A copy of the signed and dated information and consent should be provided to the patient prior to participation.

If the patient or legally acceptable representative is unable to read, a reliable, impartial, and independent witness should be present during the entire informed consent discussion. The choice of the witness must not breach the subject's right to confidentiality. A reliable independent witness is defined as one not affiliated with the institution or engaged in the investigation. A family member or acquaintance is an appropriate independent witness. After the subject or legally acceptable representative verbally consents and has signed, if capable, the witness should sign and personally date the consent form attesting that the information is accurate and that the subject or legally acceptable representative has fully understood the content of the informed consent agreement and is giving true informed consent.

Also, patient will be informed in a timely manner whenever new information becomes available that may be relevant to the patient's willingness to continue participation in the study; the revised informed consent form containing such information is to be provided to the patient, and communication of this information will be documented.

#### **8.4 Compensation to Subjects**

The patients will not receive payment for taking part in the study. Patients who are entitled to discounted or free health care, e.g. civil servants, will receive their entitled free treatment as normal. The study is covered by an insurance policy managed by the Clinical Trial Centre of The University of Hong Kong, in which to cover claim by, or compensation for, patients treated in study.

#### **8.5 Ethics Committee or Institutional Review Board**

Prior to commencement of the study, the study protocol will be submitted together with its associated documents (patient information, consent form, IB) to the IRB/EC for their favourable opinion. The favourable opinion/approval of the IRB/EC will be filed in the study file. The study will only commence following provision of a written favourable opinion.

Any amendments to the protocol will be submitted to the IRB/EC and they will be informed about SAEs in accordance with national and/or local requirements.

#### **8.6 Role of Funding Source**

The study drug and partial funding will be provided by Merck Healthcare KGaA, Darmstadt, Germany. The Funder otherwise has no role in study design, data collection, data analysis, data interpretation, or in the writing of the study report. The Funder will review the manuscript before submission for publication.

#### **8.7 Publication Policy**

The results of this study may be published or presented at scientific meetings. The Sponsor will comply with the requirements for publication of study results in accordance with standard editorial and ethical practice.

The Sponsor agrees to submit all manuscripts or abstracts to the Funder for review before submission for publication. This allows the Funder to protect proprietary information and to provide comments.

Authorship will be determined by mutual agreement and in line with International Committee of Medical Journal Editors authorship requirements.

## **9 STUDY MANAGEMENT**

### **9.1 Data Quality Assurance**

The main objective is to obtain those data required by the study protocol in a complete, accurate, legible and timely fashion. The data in the CRF should be consistent with the relevant source documents.

The CRFs must be filled in completely and legibly (with either black or blue ballpoint pen, acceptable for use on official documents). Any amendments and corrections necessary must be undertaken and countersigned by the Investigator(s), stating the date of the amendment/correction. Errors must remain legible and may not be deleted with correction aids (e.g., Tipp-Ex®). The Investigator(s) must state his/her reasons for the correction of important data. In the case of missing data/remarks, the entry spaces provided in the case report form should be cancelled out so as to avoid unnecessary follow-up inquiries.

CRF entries will be done by the study team and checked against source documents, except for the pre-identified source data directly recorded in the CRF. The Informed Consent Form will include a statement by which the patient allows the Sponsor's duly authorized personnel, the Ethics Committee (IRB/EC), and the regulatory authorities to have direct access to source data which support the data on the CRF. Such personnel, bound by professional secrecy, must keep confidential all personal identity or personal medical information (according to confidentiality rules).

### **9.2 Direct Access to Source Data/Documents**

For the purpose of ensuring compliance with the clinical study protocol, Good Clinical Practice and applicable regulatory requirements, the Investigator(s) shall permit auditing by the Sponsor, the Funder, and inspection by applicable regulatory authority.

The Investigator(s) agree(s) to allow the auditors/inspectors to have direct access to the study records for review, being understood that these personnel is bound by professional secrecy, and as such will not disclose personal identity or personal medical information.

The Investigator(s) will make every effort to help with the performance of the audits and inspections, giving access to all necessary facilities, data, and documents.

As soon as the Investigator(s) is/are notified of a future inspection by the authority, he will inform the Sponsor and the Funder.

The confidentiality of the data verified, and the protection of the patients should be respected during these inspections.

Any result and information arising from the inspections by the regulatory authority will be immediately communicated by the Investigator(s) to the Sponsor and the Funder as per timeframe stipulated in the ISS agreement.

The Investigator(s) shall take appropriate measures required by the Sponsor to take corrective actions for all problems found during the audit or inspections.

